# **List of Abbreviations and Acronyms**

ART Anti-Retroviral Therapy

BMI Body Mass Index

BRTI Biomedical Research and Training Institute

BVI Body Volume Index

CBO Community-Based Organisation
CHW Community Health Worker
CT Chlamydia Trachomatis
GC Neisseria gonorrhoeae

GCLP Good Clinical Laboratory Practice

GCP Good Clinical Practice HCW Health Care Worker

HIV Human Immunodeficiency Virus HTC HIV Testing and Counselling

IEC Information, Education and Counselling

IPC Infection Prevention and Control

IPV Intimate Partner Violence IRB Institutional Review Board

LARC Long Acting Reversible Contraception

LSHTM London School of Hygiene and Tropical Medicine

mHealth Mobile Health

MHH Menstrual Health and Hygiene

MOHCC (Zimbabwe) Ministry of Health and Child Care

MOPSE (Zimbabwe) Ministry of Primary and Secondary Education

MRCZ Medical Research Council of Zimbabwe

MUAC Mid-upper arm circumference NGO Non-Governmental Organisation

OMT Oral Mucosal Test

PITC Provider-initiated HIV testing and counselling

PLHIV People Living With HIV
PrEP Pre-Exposure Prophylaxis
RCT Randomised Controlled Trial
RCZ Research Council of Zimbabwe

RDT Rapid Diagnostic Test

SAC Scientific Advisory Committee

SDF Silver Diamine Fluoride SMS Short Messaging Service

SRH Sexual and Reproductive Health

SSA Sub-Saharan Africa

STI Sexually Transmitted Infection

UK United Kingdom

UNAIDS United Nations Programme on HIV/AIDS

VMMC Voluntary Male Medical Circumcision

WHO World Health Organization
YAG Youth Advisory Group

YFHS Youth Friendly Health Services

YP Young People

# **Executive Summary**

In adolescence, health-related behaviours are adopted that will have substantial positive or negative impacts on the individual's short- and long-term health, educational attainment, and employment prospects. However, few adolescents have any contact with health services, especially for health promotion and disease prevention, and services are not always appropriate for their needs.

**Aim:** To develop, implement and evaluate the acceptability, feasibility, effectiveness, and cost-effectiveness of a potentially sustainable adolescent health and well-being check-up programme in Zimbabwe to improve health and well-being.

#### Design:

The study comprises: Phase 1: Development and piloting; Phase 2: Implementation and evidence generation; Phase 3: Knowledge dissemination and translation. Outputs will be (i) a novel intervention to improve adolescent health and well-being, (ii) evidence in urban settings in Zimbabwe on the interventions feasibility and cost-effectiveness, (iii) guidelines for implementation and evaluation in Zimbabwe and in other LMICs, and (iv) proposals for follow-on studies in Zimbabwe and other LMICs.

**Intervention:** The Y-Check strategy will involve the screening and treatment/referral of adolescents for important conditions through health check-up visits at two key time points during adolescence: early adolescence (10-14y) and mid/late adolescence (15-19y). Adolescents will only be screened for conditions with an accurate and acceptable screening test and a locally-accessible effective intervention e.g. mental health, HIV, vision, hearing, and anaemia. The package of services will include risk reduction counselling and general health information and counselling.

**Study Outcomes:** In this hybrid effectiveness-implementation study, both implementation process and adolescent outcomes will be captured. The primary outcome will be the proportion of those screening positive for at least one condition who receive appropriate on-the-spot care or complete appropriate referral within 4 months. Secondary outcomes will include yield of previously undiagnosed and un-referred conditions; intervention acceptability, adoption, appropriateness, feasibility, fidelity, and cost; reported health-related risk and protective behaviours; engagement with health services; well-being; clinical and educational outcomes.

**Study population:** The intervention will be delivered to 1000 10-14 year old males and females and 1000 15-19 year old males and females. An initial pilot study of around 200 participants will be conducted before the main intervention, taking the total number of participants to 2200. Parents, carers and other stakeholders (teachers, service providers, community leaders etc.) will participate in study development and evaluation workshops and interviews.

**Study duration and sites:** The planned duration of the entire study will be 4 years. The two age cohorts will be recruited in year 2 and followed for approximately 12 months. The study will be conducted in 4 communities, up to 8 secondary schools, and up to 6 primary schools in Chitungwiza, Harare Province, Zimbabwe.

**Risk-benefit assessment:** The risks and benefits of the Y-Check intervention will be described to participants and their parents/guardians during the consent process. Y-Check participants

will benefit from early detection of health problems, health promotion, and the development of health-seeking behaviours. However, some conditions such as HIV and sexually transmitted infections (STIs), which will be screened for, are associated with stigma and anxiety. The Y-Check team will be trained in good clinical practice, data protection and confidentiality, and will provide counselling for participants testing positive for any conditions. Furthermore, the protocols and procedures for communicating with adolescents and their families will be carefully developed in collaboration with the Youth Advisory Group (YAG) and community stakeholders.

Figure 1. Overview of Study Design

Chitungwiza, Harare Province, Zimbabwe

Y-Check 1 (YC1, 10-14 y): 4-6 schools

1000 males & females

Y-Check 2 (YC2, 15-19 y): 2-8 schools and 2 community venues 1000 males & females

Y-Check 1 & Y-Check 2 schools only: Whole class education sessions

Supportive
environment for
behaviour change
and service
uptake
Community &
School
engagement

Quality health
service provision
Training at
health facilities

#### Y-CHECK INTERVENTION (30-60 minute screening visit) Registration, health information

**Pre-consultation questionnaire:** Psychosocial issues, alcohol, tobacco, and substance use, physical activity and diet, oral health, mental health and well-being, male circumcision and sexual activity, immunisation, epilepsy

**Physical examination & laboratory:** Anthropometry, oral examination, eyesight, hearing, physical impairment, anaemia, schistosomiasis, HIV (YC2), Blood pressure (YC2), STIs (YC2)

Nurse review & intervention: Iron and folic-acid supplementation, SDF (for teeth), MHH products, STI treatment (YC2), contraception (YC2), condoms (YC2), PrEP (YC2), counselling, referrals (social services, youth friendship bench, food supplementation services, dentist, hearing/eyesight NGOs, physiotherapist, VMMC, HIV treatment and care),

Collection of cost and process data; review of health and other service utilisation data

4-month and 12-month follow-up visits: Adolescent questionnaire & repeat of screening visit

Primary implementation outcome: % of those screening positive for at least one condition who receive appropriate on-the-spot care or complete appropriate referral for all identified conditions within 4 months

#### Secondary implementation outcomes

- Yield of previously undiagnosed and un-referred conditions
- Acceptability (satisfaction): acceptable to adolescents and stakeholders
- Adoption (uptake, utilisation, intention to try): screening uptake, referrals completed
- · Appropriateness (perceived fit, relevance, usefulness): perceived value of services
- Feasibility (actual fit, practicability): referrals completed, community support
- · Fidelity (adherence, integrity, quality): diagnostic accuracy, YFHS quality
- Implementation cost: cost per condition identified and treated/referred

#### Secondary client outcomes

- · Knowledge about health services and health behaviours
- · Agency to make decisions about health
- Self-esteem, Well-being
- Reported health-related risk and protective behaviours
- · Reported engagement with health services
- Clinical outcomes
- · Educational outcomes
- Client-centered outcomes (to be defined during Phase 1)
- Cost-effectiveness: cost per improvement in well-being and per DALY/QALY averted

# 1. Introduction

To unlock human potential and accelerate progress towards achieving the Sustainable Development Goals (SDGs), it is essential to improve the health and well-being of adolescents (10-19 years). Health is an essential component of human capital, yet adolescent investments have focused primarily on education with little attention to synergies between health and education. Research investments in the first 1000 days of life have dramatically outweighed investments in the subsequent 7000 days, leaving an evidence-gap on how to develop and sustain human potential through adolescence and early adulthood.

Among adolescents in African low and middle-income countries (LMICs), HIV and iron-deficiency anaemia are among the top five causes of adolescent disability-adjusted life years (DALYs) lost, with poor mental health, poor diet, low physical activity, and alcohol use among the leading risk factors for death. Adolescents with disabilities are particularly vulnerable and face a range of challenges in achieving their full capabilities. Identifying adolescents with risky conditions and behaviours or undiagnosed disability is important given (i) the growing number of adolescents (ii) the increasing proportion of the total burden of disease that occurs in adolescence and (iii) the fact that many key health conditions (e.g. mental health disorders) and behaviours (e.g. tobacco and alcohol use, unhealthy diet, low physical activity, risky sexual behaviours) that predispose to serious conditions in later life start in adolescence (iv) the negative impact of poor health on educational attainment.

Systematic reviews have identified individual interventions that are effective at improving various aspects of adolescent health, however, most adolescents only come in contact with health services when they are ill, and services are not always appropriate for their needs. This represents a missed opportunity for early detection of health problems, health promotion, and the development of healthy health-seeking behaviours. Early and sustained engagement with health services could reap a triple dividend for human development by improving the health of adolescents, their health in adulthood and the health of their future offspring. 

Routine health check-up visits for adolescents which screen for multiple conditions and risk behaviours, could provide an entry point into services and be highly cost-effective, but there is little empirical evidence for their feasibility, acceptability and effectiveness. Many high-income countries have national recommendations related to adolescent health check-ups (largely based on expert opinion). In low and middle income settings, preventative health services for adolescents are largely provided in schools, are usually limited to deworming and vaccination campaigns, and do not address other important conditions and risk factors such as nutrition, mental health, and disability. Obtaining evidence on check-ups is a top World Health Organization (WHO) priority for adolescent health research so that they can develop recommendations for preventive and promotive contacts with the health system for adolescents.

The 2018 Zimbabwean School Health Policy, jointly authored by the Ministry of Health and Child Care (MoHCC) and the Ministry of Primary and Secondary Education (MoPSE), provides a policy framework for the provision of comprehensive school health programming. This policy provides a framework for the implementation of health education and promotion including screening for communicable and non-communicable diseases, immunization campaigns, mass drug administration (e.g. for bilharzia and soil-transmitted helminths), growth monitoring and assessments, and nutritional services. In this policy the government confirms their commitment to providing school health services

in order to optimise educational outcomes and contribute towards the broader National development objectives.

The programme (Y-Check) will therefore, address a critical gap in the field of adolescent health and will provide policy relevant evidence on check-up visits and the implementation of school health services. Y-Check will screen and treat/refer adolescents for common conditions through health check-up visits in younger (10-13y) and older (16-19y) adolescents. Adolescents will only be screened for conditions that have an accurate and acceptable screening test and a locally accessible effective intervention e.g. mental health, HIV, vision and hearing impairments, anaemia. Human-centred design will be used to develop the intervention, including the content and mode of delivery of the intervention, to address the supply and demand barriers to services.

The conceptualisation of an adolescent health check-up programme was the focus of a WHO-convened, DFID-funded multi-country workshop in Zimbabwe in 2018. WHO, London School of Hygiene & Tropical Medicine (LSHTM), Biomedical Research and Training Institute (BRTI) and collaborators subsequently obtained funding from Fondation Botnar for formative work (August 19-October 20, PI: [name] (WHO)) to develop the content and format of a programme in Zimbabwe, Ghana, and Tanzania. The Zimbabwean situation analysis involved a document review, and in-depth interviews and participatory workshops in Chitungwiza. The document review showed the lack of any routine health check-ups and the absence of age-disaggregated prevalence data for many health conditions. 

In-depth interviews and participatory workshops with adolescents, parents of adolescents and key stakeholders (MoHCC, MoPSE, Community Based Organisations (CBOs), healthcare workers and specialists) found that there was overall support for the introduction of routine health check-ups. To navigate potential barriers, stakeholders suggested clear messaging, awareness building, and sensitisation campaigns to overcome disinterest in preventative healthcare and religious messaging against healthcare engagement.

# 2. Study Aim, Objectives and Design

#### 2.1 Aim

To develop and implement a potentially sustainable adolescent health check-up programme in Zimbabwe and evaluate the acceptability, feasibility, effectiveness, and cost-effectiveness of the programme to improve health and well-being.

# 2.2 Objectives

- 1. To develop and pilot test a check-up programme for adolescents that screens for important health conditions using accurate and acceptable screening tests and provides locally-accessible effective interventions (**Phase 1**)
- 1a To develop and pilot test a Digital Health and Well-being Club for adolescents as a basis for longer-term contacts with the adolescents (**Phase 1**)
- 2. Through a prospective intervention study in selected schools and communities in Chitungwiza, Zimbabawe to (**Phase 2**):
  - i. Evaluate the **implementation of the programme** by measuring key implementation outcomes: acceptability, adoption, appropriateness, feasibility, fidelity, and cost.

- ii. Describe the programme **context** and **mechanisms of action**.
- iii. Estimate **short-term programme impact on adolescent outcomes**: health-related knowledge; intentions, agency, and perceived social support for behaviour change; engagement with health services; health-related behaviours; well-being, improvements in previously-diagnosed health and well-being conditions.
- iv. Estimate the **cost-effectiveness** of the programme in reducing overall disease burden and improving adolescent well-being
- v. **Obtain information on key parameters needed for the planning of a next phase larger evaluation study**: prevalence of health conditions and behaviours, acceptability of referral, feasibility of following-up programme participants, initial estimates of the impact of the programme on longer-term health, educational and well-being outcomes, and optimal implementation of the Y-Check intervention.
- 3. To refine the programme and its theory of change, and finalise optimal methods for the measurement of impact of the programme in future studies (**Phase 3**).

# 2.3 Study design

During **Phase 1** (**Intervention development and piloting**) we will use a variety of processes and methodologies including community engagement, participatory co-design, qualitative interviews and discussions, health register and school register review, and validation and pre-testing of screening tools, procedures and referral protocols. Locally accessible services will be identified and pre-tested to confirm that they are acceptable and accessible from multiple perspectives, including adolescents themselves. An extended period of piloting will involve the piloting of the screening tools and procedures for each of the target conditions and behaviours with revisions and repeat piloting where required. Up to 200 participants will be involved in the piloting of screening tools and procedures. There will be an opportunity for young people and stakeholders to suggest additional relevant outcomes that may reflect some of their priority concerns/intentions that should be captured (Client-centered outcomes).

During Phase 2 (Implementation and evidence generation) we will conduct a prospective intervention study (cohort study) in Chitungwiza, Zimbabwe to assess the feasibility of the intervention and to evaluate the short-term impact of the intervention. The intervention will be implemented for 10-14 year olds in 4-6 primary schools (N=1000, Y-Check 1), 15-19 year olds at 2-8 secondary schools, and 16-19 year olds at 2-4 community venues (N=1000, Y-Check 2). The intervention does not intend to target all adolescents but instead to focus on two time points during the adolescent period: early adolescence (10-14) years at or just before the onset of puberty, and middle/late adolescence (15-19 years) when many adolescents become or are soon to become sexually active. The exact target school grades and age-ranges will be agreed in consultation with MoPSE, MoHCC and other stakeholders during Phase 1 of the study.

In this hybrid effectiveness-implementation study, both data on implementation process, and adolescent outcomes will be captured. A mixed-methods process evaluation will describe the programme implementation, context, and mechanisms of action. The study cohort will be followed up for approximately 12 months with adolescent process and outcome data collected at screening, 4-month and 12-month follow-up visits (**Figure 2**). An economic evaluation will estimate unit costs per adolescent screened, condition identified and case treated, and estimate the cost-effectiveness of the intervention in improving adolescent well-being. Where data are available, we will estimate the impact

of the intervention on DALYs averted. We will gather information to develop methodologies for a potential larger future study to measure the longer-term health, well-being and educational impact of the programme. We will assess the scale up and financial sustainability of the programme.

The prospective intervention study design is more appropriate than a randomised controlled trial (RCT) for answering the research question because i) it is impossible to measure the adolescent outcomes in the absence of the screening which is an integral part of the Y-Check intervention; ii) the intervention components are known to be effective for identifying conditions for which known effective interventions exist (e.g. Provision of spectacles for adolescents with myopia; provision of psychological interventions by trained lay mental health providers through the "Friendship Bench" approach for adolescents with symptoms of significant common mental health disorders), so a control arm in which adolescents were screened, found to have these conditions but not offered care would be unethical; and iii) the great majority of conditions being screened for are chronic, so the prevalence of previously undiagnosed and untreated conditions or risky behaviours provides its own counterfactual reflecting a lack of prior appropriate diagnosis and effective treatment.

COVID-19, which the WHO declared a pandemic on 11 March 2020, has had significant effects on research activities worldwide. Over the past 18 months, adaptations to procedures have allowed research activities to continue in a safe environment for research staff and participants.

All Y-Check procedures will be conducted in well-aerated tents or outdoors to minimise risk during screening tests, physical examinations, and blood tests. Standard infection prevention and control (IPC) protocols will be implemented with all staff and participants wearing appropriate surgical or cloth masks. If a participant does not have a suitable mask, the research team will provide a new surgical mask. In addition, all staff and participants will wash their hands before interacting. Finally, all working surfaces and instruments will be sanitised between each participant. If standard COVID-19 IPC protocols cannot be implemented in school settings, the Y-Check service will be temporarily delivered in the community until a suitable solution is found.

If there is a suspected COVID case, we will follow the national guidelines that are current at the time. Y-Check will use opportunity to advocate for all adolescents who are eligible for Covid-19 vaccination locally who attend the Y-Check-Up to avail themselves of this opportunity and will provide information on where they might go to get vaccinated.

Social distancing, handwashing, and sanitisation of surfaces will also be implemented during all interviews and focus group discussions.

**Phase 3 (Knowledge dissemination and translation)** will involve statistical analysis, mathematical modelling, refinement of programme guidelines, report writing, dissemination of study findings to young people and other stakeholders, and the development of research proposals.

Figure 2: Timeline of Study

	2021			2022			2023				2024					
	Q1	Q2	Q3	Q4	Q1	Q2	Q3	Q4	Q1	Q2	Q3	Q4	Q1	Q2	Q3	Q4
Inception	*	*														
Intervention development and pilot testing			*	*	*	*										
Implementation of Y-Check							*	*	*	*						
Research cohort recruitment							*	*	*	*						
Follow-up at 4 & 12 months								*	*	*	*	*	*	*		
Process and economic evaluation							*	*	*	*	*	*	*	*		
Analysis & reporting													*	*	*	*

[figure not shown]

Figure 3: Y-CHECK logic model

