#### 3.1 Target conditions and behaviours

Informed by a scoping literature review and expert consultation during the 2019/20 formative work, conditions and behaviours were selected based on their prevalence, and the ability to diagnose and treat. The conditions and behaviours to be screened for and the rationale for their choice is summarised in **Table 1**. The target health conditions and behaviours will be finalised towards the end of Phase 1 following additional stakeholder engagement and pre-testing of screening tools and referral pathways (see section 5.1).

Table 1: Rationale for choice of conditions and behaviours included in checkup visit.

	Rationale				
Psychosocial issues	The quality of an adolescent's home and working/school life, and their				
(difficult home	relationship with their peers can impact on their mental health.				
environment, challenges	Identifying and helping adolescents who are living in difficult situations				
with education or	will improve their health and well-being.				
employment, participation					
in social activities, and					
safety and security)					
Drug, alcohol and tobacco	Risk behaviours often start in adolescence and contribute to morbidity				
use	and mortality in adolescence as well as increasing later risk of NCDs				
Mental Health	Identified as a leading cause of morbidity among adolescents and is				
	associated with suicide and increased risk behaviours.				
Growth, nutrition, and	Poor nutrition in adolescence can affect health and well-being, adult				
physical activity	body size, and may also affect the nutritional status of children born to				
	women who were malnourished in adolescence.				
	Obesity and lack of exercise in adolescence are risk factors for NCDs in				
	adulthood.				
Anaemia	Anaemia is a leading cause of morbidity among adolescents.				
Oral health	Untreated dental cavities can cause severe pain, infection, and problems				
	with eating, speaking, and learning in children and adolescents. 				
	Risk reduction counselling is insufficient without the availability of				
SRH & HIV prevention	HIV prevention commodities.				
	Provision of MHM and other SRH products enhances acceptability by				
	community and adolescents.				

	Testing for STI's important as syndromic management not very effective.					

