## **Prospective Intervention study**

We will follow the STROBE guidelines for the reporting of cohort studies. We will create a flowchart showing the number of communities and schools and the number of participants per community and school at each contact point in the cohort study. We will use descriptive analysis to compare the community-level and school-level characteristics of the four study communities and schools.

The primary outcome is a single proportion which will be presented with a 95% confidence interval for each of the 4 target populations: 10-13y male, 10-13y female, 16-19y male, 16-19y female. Secondary outcomes which are measured at a single time point will be presented in a similar way. For outcomes which are measured at two or more time-points, a before-after analysis will be conducted comparing differences in measures between the two time-points. The unit of analysis will be the individual. For clinical outcomes which are measured at two or more time-points, the initial check-up visit (baseline) will give the prevalence of undiagnosed and untreated chronic conditions which will represent the counterfactual. The proportion of undiagnosed and untreated chronic conditions at the 4-month follow-up visit will be formally compared to this counterfactual to estimate the effectiveness of the intervention in improving these clinical outcomes. We will assess health service and client determinants of correct management of conditions at 4 months using multivariable regression.

**Digital platform data** De-identified data on information viewed, games played, rewards provided/used along with programmatic data on behaviours and clinical conditions etc. will be analysed using machine learning approaches to understand the sub-groups/segments of adolescents who participate in Y-Check. This analysis will help us to define, develop, and pilot test targeted messaging for different sub-groups of young people who attend Y-Check follow-up visits. We will also analyse this data to develop algorithms which could potentially be used in the future phases of the Y-Check programme to further personalise the Y-Check user experience to maximise relevance, uptake and retention.

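### Section 2.3 treats baseline as the counterfactual for risky behaviours, but the protocol says these behaviours start in adolescence, so a before-after change in them is not a programme effect

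*Protocol*

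**What the plan says.** Section 2.3 gives three reasons for preferring a single-cohort intervention study to a randomised trial. The third starts from the premise that "the great majority of conditions being screened for are chronic" and concludes: "so the prevalence of previously undiagnosed and untreated conditions or risky behaviours provides its own counterfactual".

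Elsewhere the protocol describes when risk behaviours begin:
- Section 1 refers to "behaviours (e.g. tobacco and alcohol use, unhealthy diet, low physical activity, risky sexual behaviours) that predispose to serious conditions in later life start in adolescence".
- Table 1 (section 3.1), on drug, alcohol and tobacco use, says: "Risk behaviours often start in adolescence".
- Section 2.3 describes the older target group as "middle/late adolescence (15-19 years) when many adolescents become or are soon to become sexually active".

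Health-related behaviours are listed under short-term programme impact in objective 2.iii (section 2.2). Reported risk and protective behaviours are a secondary client outcome in section 6.1. Appendix 1 names alcohol, tobacco and substance use, frequency of unprotected sex and modern contraceptive use among them. On timing, section 2.3 says: "The study cohort will be followed up for approximately 12 months with adolescent process and outcome data collected at screening, 4-month and 12-month follow-up visits".

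For any outcome measured at two or more time-points, section 6.3 says "a before-after analysis will be conducted comparing differences in measures between the two time-points", with the individual as the unit. It then names baseline as the counterfactual for clinical outcomes only, as the prevalence of undiagnosed and untreated chronic conditions, and formally compares that with the 4-month value.

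**The concern.** Baseline can stand in for the untreated follow-up value only if the outcome would have stayed put without the programme. For an untreated chronic condition that is arguable. For a behaviour that is still being taken up it is not, and the protocol itself says these behaviours are taken up at these ages. The premise in section 2.3 concerns conditions, while the conclusion reaches behaviours as well.

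What is at stake is how the behavioural results under objective 2.iii are read. A raw change would combine what Y-Check did with what some months of adolescence did. A real reduction could appear as no change or as harm, or natural change could be credited to the programme. Objective 2.v uses the study to plan a larger evaluation, so a misread change could carry forward.

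**Working it through.** **Step 1: premise against conclusion.** The premise is chronicity of conditions. The conclusion covers conditions and risky behaviours. No statement that behaviours are stable is offered, and the three places quoted above say that they start in this age range. The conclusion therefore does not follow for behaviours.

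**Step 2: does it reach the analysis?** Section 6.3 applies its formal counterfactual comparison to chronic clinical conditions. Behaviours fall under the general before-after sentence, which names no comparator. So section 2.3 is wider than section 6.3, but behaviours still receive an uncontrolled before-after comparison in service of an impact objective.

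**Step 3: size in the whole cohort.** The protocol gives neither baseline prevalence nor onset rates for behaviours, so there is no figure to reproduce and all rates below are assumptions. Let p0 be baseline prevalence and a the 12-month onset among those without the behaviour, ignoring cessation.

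Untreated follow-up = p0 + (1 − p0)a, so the before-after change = true effect + (1 − p0)a.

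The added term (1 − p0)a, in percentage points:

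| p0 | a = 2% | a = 5% | a = 10% |
|---|---|---|---|
| 5% | 1.9 | 4.75 | 9.5 |
| 10% | 1.8 | 4.5 | 9.0 |
| 20% | 1.6 | 4.0 | 8.0 |

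If onset were spread evenly over the year, the 4-month term would be about a third of this: 1.6/3 ≈ 0.5 to 9.5/3 ≈ 3.2 points.

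Worked case: p0 = 10%, a = 5%, and a programme that lowers follow-up prevalence by a relative 20%. Untreated follow-up is 0.10 + 0.90 × 0.05 = 14.5%. Observed follow-up is 0.8 × 14.5% = 11.6%. The before-after change is +1.6 points, while the true effect is 11.6 − 14.5 = −2.9 points. A benefit reads as a small harm.

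**Step 4: adding cessation.** With an assumed 10% cessation among baseline users, the expected drift becomes (1 − p0)a − 0.10p0. A simulated paired (McNemar) test used 1000 participants (one age group with complete follow-up), no programme effect, a two-sided 5% level and 20,000 runs:
- Onset 5%: a significant rise in about 75% of runs at p0 = 20%, and in practically all at p0 = 5%.
- Onset 2%: a significant rise in about 85% of runs at p0 = 5%. At p0 = 20% the drift is 1.6 − 2.0 = −0.4 points, with a significant rise in 0.4% of runs and a significant fall in 9%.

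Even in the whole cohort, the sign depends on whether onset outweighs cessation.

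**Step 5: denominator restricted to baseline positives.** Baseline is then 100% by construction, and onset cannot contribute. With the same assumed 10% cessation and no programme effect, follow-up is 90%: an apparent fall of 10 points against a true effect of zero. Regression to the mean in self-report pushes the same way. The bias now looks like benefit.

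**Step 6: which denominator applies?** The protocol does not say for behaviours. Section 6.1 lists them without one. Section 4.3.2 refers to clinical outcomes among those who screen positive, and Appendix 1 ties its secondary outcomes to managed conditions.

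**The case against.** The strongest reply is that section 6.3, where the analysis is set, already confines the formal counterfactual to chronic clinical conditions at 4 months. On this view the fault is three words in a design rationale, and any age adjustment for secondary outcomes belongs in a statistical analysis plan that is not shown. The first part stands and narrows the point. The second stands as far as it goes: the lack of an age term is not the finding. But the sentence in section 2.3 is a positive statement offered as a reason for having no control arm, and no analysis plan can make it true for behaviours. Objective 2.iii still asks for impact on them.

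It is also fair to say that starting in adolescence does not by itself establish a material rise within 4 months, that every rate above is assumed, and that the direction depends on an unstated denominator. A reader might infer that the bias always masks benefit, or that it has a known size. The documents support neither.

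A reader might also infer that an age-matched model should replace the before-after comparison. That goes too far. School recruitment is by grade, and section 3.7 notes that over-age pupils started late or repeated years, so age within a grade carries schooling history. The oldest participants have no older baseline peers. With age in single years, about 1 − 4/12 = two-thirds of participants would stay in the same category at 4 months, so such a term would miss most of the drift it is meant to remove.

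Finally, section 3.7.2 limits sexual and reproductive health services to the Y-Check 2 community hubs, so the sexual-debut and contraception example concerns only part of the cohort.

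**Conclusion.** The own-counterfactual claim in section 2.3 is unsupported for risky behaviours, because its premise covers only conditions and the protocol's account of when behaviours start contradicts it. A before-after change in these outcomes cannot be read as a programme effect under objective 2.iii.

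The size cannot be derived from the protocol. The range of 1.6 to 9.5 points at 12 months rests on assumed baselines of 5-20%, onset of 2-10%, no cessation and a whole-cohort denominator. In the whole cohort, onset tends to hide a reduction in risk behaviour or make it look like harm. For contraceptive use, a protective behaviour, uptake that follows sexual debut could look like benefit. Among baseline positives, cessation and regression to the mean tend to look like benefit.

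The reach is limited. The primary outcome, a single proportion, is untouched, and so is the formal comparison for chronic clinical conditions in section 6.3. A reader might infer that the whole rationale for an uncontrolled design fails. The point does not show that: it concerns the extension to behaviours, and the other two reasons in section 2.3 do not depend on it.

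**What to change.** 1. **Section 2.3:** delete the three words that add risky behaviours to the own-counterfactual sentence, so that it agrees with section 6.3.
2. **Section 6.3:** state that before-after changes in age-emergent behaviours (alcohol, tobacco and substance use, unprotected sex, contraceptive use) are descriptive and are not estimates of programme effect.
3. **Supportive analysis only:** fit a model with age at measurement as a continuous term (from the date of birth recorded at registration), sex, setting (school or hub) and a before/after term, restricted to ages with baseline overlap. State its limits with it: wider intervals, and the assumption that neighbouring ages within a setting are comparable, which over-age pupils within a grade may violate.

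Items 1 and 2 cost a few words and need no new data. Item 3 uses data already planned and costs some precision. If it is not wanted, items 1 and 2 alone cure the main fault. The price is that the study would describe behaviour change without claiming impact on these behaviours, so objective 2.iii should be read in that light.
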